Protocol version 1.0 dated 29/10/2018

Sponsor: University Hospitals of Leicester

Background

Even a simple local anaesthetic procedure is associated with much anxiety for the patient involved. This is compounded by the process of local anaesthetic injection which involves not only the pain of the needle puncture but the stinging sensation as the local anaesthetic is infiltrated into the site. Many methods of easing this pain have been used such as using smaller gauge needles, slow infiltration, buffering the anaesthetic and prior application of local anaesthetic creams.

There has been a lot of research conducted in dentistry which has shown the effectiveness of Transcutaneous Electronic Nerve Stimulation (TENS) as an anaesthetic agent. But the research has not extended to other fields of surgery such as in minor local anaesthetic cases.

Aim

TENS-LA trial will be able to provide evidence regarding the possible efficacy of TENS as a local anaesthetic and its ability to alleviate the pain associated with local anaesthetic injection. The effectiveness will also be compared to that of local anaesthetic cream which is being used at present prior to local anaesthetic injections.

Outcome

Primary Outcome: The primary outcome is pain of local anaesthetic injection after application of TENS or LA cream as measured by two Numeric Pain Rating Scale Secondary Outcomes: Changes in blood pressure and pulse rate in response to injection of local anaesthetic

Trial Design

A prospective randomised controlled trial.

Diagnosis and Inclusion/Exclusion Criteria

Adults 18-90 years of age undergoing a split skin graft harvest from the thigh under local anaesthesia will be included

- who do not have a pacemaker or ICD
- who are not pregnant
- with no history of epilepsy, aneurysm
- with no history of allergy to local anaesthetic or TENS electrodes

Test device and Mode of usage

A hand-held battery-powered CE-approved TENS device will be used. Eligible patients who have been randomised to the test arm of the study will have the electrodes attached to the area adjacent to the skin graft donor site 30 minutes before injection of local anaesthetic.

Setting

The trial will be conducted in Leicester Royal Infirmary, UK

Duration of treatment

The TENS treatment is over a minimum period of 30 minutes from attachment of electrodes to administration of local anaesthetic.

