2. TRIAL DESIGN

2.1 OVERVIEW

Flow Chart: Study Overview

Eligibility

Adult undergoing a split skin graft harvest

- Between 18 and 90 years of age
- Not having a pacemaker or ICD
- Not pregnant
- Not mentally incapacitated
- No history of epilepsy or aneurysm
- No history of allergy to LA or TENS electrodes
- No history of undiagnosed skin/pain conditions
- Not taking part in other trials

Appropriate CONSENT process

RANDOMISE

(TENS/EMLA)
BP and pulse recording

Apply TENS/EMLA

Administer LA injection (30 minutes after TENS, 60 minutes after EMLA)
Record BP and Pulse before injection.

Complete Numeric pain rating scale and BP and Pulse chart

TENS-LA trial is a randomised control trial to assess the possible efficacy of Transcutaneous Electrical Nerve Stimulation (TENS) on eliminating or reducing the pain of local anaesthetic injection for minor surgical procedures. Comparison is done with a mixture of local anaesthetic cream (EMLA) which is used at times for the same purpose. Though local procedures are carried out in various parts of the body, this trial will be conducted specifically on patients undergoing a split skin graft harvest from the thigh. Patients who meet the eligibility criteria and are willing to participate will be randomised to receive either TENS or EMLA.

Eligible patients: Adult patients listed to have a split skin graft harvest under local anaesthesia will be assessed for eligibility for taking part in the trial.

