2.3 SAMPLE SIZE

The study is designed to detect a difference of 3 units in pain scale between the 2 groups at 0.05 significance level and 90% power. We assume the standard deviation as 3 and the number of participants in each group has been calculated as 22. The total number of the patients including both arms of the trial will be 44.

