2.13 ANALYSIS

The analysis will assess the effectiveness of TENS in alleviating the pain of local anaesthetic injection with the differentiation of needle and infiltration pain and also compare the TENS with EMLA. It is expected that TENS will alleviate or bring about a significant reduction in the pain associated with injection of local anaesthetic and will be better or as effective as EMLA in this aspect. This is the hypothesis being examined in this trial.

Pain perception will be evaluated using two Numeric Pain Rating Scales in the study and control groups. Pulse rate and Blood Pressure monitoring will be carried out as an objective measurement of response to pain.

The tabulation of the results will be done by the research team after transcribing to an excel spreadsheet and the fully anonymised data will be analysed statistically by the biostatistician at The University of Leicester.

Summary statistics of 2 groups will be presented. Median score, lower and upper quartile and minimum and maximum scores will be given for each group. Two groups will be compared using Mann Whitney test.

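### The first blood pressure and pulse reading follows randomisation with no blinding described, and the one named test, if it also covers these outcomes, uses no baseline covariate

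*Protocol*

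**What the plan says.** The synopsis of the protocol (Outcome) gives the secondary outcome as "Changes in blood pressure and pulse rate in response to injection of local anaesthetic".

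The flow chart in section 2.1 has three recording points:

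1. Below the randomisation step and above application of the treatment: "BP and pulse recording".
2. After treatment, 30 minutes for TENS or 60 for EMLA: "Record BP and Pulse before injection".
3. At the end: "Complete Numeric pain rating scale and BP and Pulse chart". The timing of this last reading relative to the injection is not given.

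Section 2.13 says "Pulse rate and Blood Pressure monitoring will be carried out as an objective measurement of response to pain" and attaches no test to that sentence. Its last paragraph promises "Median score, lower and upper quartile and minimum and maximum scores will be given for each group" and then "Two groups will be compared using Mann Whitney test". No outcome is tied to the test, and no covariate is named for any outcome.

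Section 1 (Methods and design) and section 2.8 describe arms that look and feel different, electrodes with current against a cream. No sham or blinding is described. Under section 2.7 the allocation is held in sealed envelopes.

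**The concern.** Blood pressure and pulse are the only measures that the protocol calls objective, and they stand beside a pain score reported by patients who can tell which treatment they have. They support the pain result best if at least one reading cannot have been influenced by the allocation. As drawn, there is none. The first reading comes after randomisation, when nothing in the protocol keeps the allocation from the patient. The second comes after the treatment itself. The protocol's own background stresses how anxious these patients are, and anticipation can move both pulse and blood pressure.

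The analysis section adds a smaller problem. If the single named test is meant for these outcomes too, readings that the trial already collects are not used as covariates, and the test alone gives no adjusted difference in mmHg or beats/min with a confidence interval. At 22 per arm, chance differences at baseline will not be rare.

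**Working it through.** **The plan's own figure.** Section 2.3 sizes the trial on pain only: it is "designed to detect a difference of 3 units in pain scale between the 2 groups", with SD 3, significance level 0.05 and 90% power. Two-sided, n = 2 × (1.960 + 1.282)² × 3²/3² = 21.0, rounded up to 22 per arm. The figure reproduces. It says nothing about blood pressure or pulse, for which no SD, correlation or power is stated.

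**Order of readings.** The flow chart runs: randomise, first reading, apply treatment, wait 30 or 60 minutes, second reading, inject, complete the pain scales and chart. Neither reading before the injection precedes randomisation.

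**Precision of adjustment.** Assume equal variance s² before and after, and correlation r between the pre-randomisation and post-injection readings. Per patient:

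- change score: 2s²(1 − r)
- ANCOVA: s²(1 − r²)
- ratio, ANCOVA to change: (1 + r)/2

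The equivalent change-score sample size per arm is 22 × 2/(1 + r). The last two columns are simulated power at 22 per arm (4000 runs, normal data, covariate unaffected by treatment), with the effect set so that a z-test on the change has 80% power.

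| r (assumed) | Variance ratio | SE reduction | Equivalent n per arm | Power, Mann-Whitney on change | Power, ANCOVA |
|---|---|---|---|---|---|
| 0.5 | 0.75 | 13.4% | 29.3 | 0.76 | 0.87 |
| 0.7 | 0.85 | 7.8% | 25.9 | 0.76 | 0.83 |
| 0.8 | 0.90 | 5.1% | 24.4 | 0.77 | 0.82 |
| 0.9 | 0.95 | 2.5% | 23.2 | 0.76 | 0.79 |

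**Chance imbalance.** The standard error of a baseline difference is √(2/22) = 0.30 SD, so a larger imbalance is expected in about a third of trials. The change-score and ANCOVA estimates then differ by (1 − r) times the imbalance. For an imbalance of 0.30 SD that is 0.15 SD at r = 0.5 and 0.03 SD at r = 0.9.

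**Which reading can be the covariate.** With equal variances the ANCOVA slope is r. Suppose treatment shifts the pre-injection reading by d and the response to injection is the same in both arms, so that the post-injection means also differ by d.

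- Change from the pre-injection reading: d − d = 0, which is correct for the response to injection.
- ANCOVA on the pre-injection reading: d − rd = (1 − r)d. With d = 0.5 SD and r = 0.5, this is a spurious 0.25 SD.

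The pre-injection reading is therefore unsafe as the main covariate. The pre-randomisation reading has no such problem, because treatment cannot have affected it. Adjusting for it estimates the effect of the allocated treatment on the post-injection level, including any effect present before the injection. That is a different question from the response to injection, so the two analyses belong side by side.

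**Why the present first reading is not clean enough.** Suppose knowledge of the allocation shifts it by a in one arm and the shift fades before the last reading. Using it as covariate would then move the adjusted difference by −ra. The protocol gives nothing from which to size a.

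**The case against.** The case against has several parts, and much of it stands.

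- **Scope of the test.** A reader might infer that blood pressure and pulse are to be compared by Mann-Whitney. Section 2.13 does not say so. The sentence follows a description of scores, which is pain-scale language, and the inference rests only on no other test being named. If the test covers pain alone, the protocol is merely silent on the model for a secondary outcome. That is commonly left to an SAP and would be no fault.
- **Baseline already used.** A reader might also infer that baseline information is thrown away. It is not: the stated outcome is a change, which already subtracts an earlier reading. Only the further gain from regression adjustment is forgone.
- **Size.** Nothing fixes r. If it is near 0.9, the gain is 5% of variance and about 3 points of power.
- **Knowledge of allocation.** A reader might take the flow chart to show that patients know their arm at the first reading. The protocol does not say when they learn it. Nor is that reading the natural reference for a response to injection; the pre-injection reading is.
- **Units.** If section 2.13 applied to blood pressure, its group medians and quartiles would be in mmHg, and a shift estimate could accompany a rank test.

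What survives is the order of the readings. That is protocol content, and no SAP can repair it once the data are collected. The uncertain scope of the named test also survives.

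**Conclusion.** The point holds in a limited form. The first reading follows randomisation, no blinding is described, and so no reading is guaranteed free of knowledge of the allocation. Whether any reading is in fact affected cannot be determined from the protocol. The only between-group test named, if it extends to blood pressure and pulse, uses no baseline covariate.

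The analysis half is a modest matter of precision: a variance reduction of 25% at r = 0.5, 10% at r = 0.8 and 5% at r = 0.9. It rests on equal variances, an assumed r, a covariate taken before randomisation, and a final chart that holds a post-injection reading. These figures compare ANCOVA with a change from that same pre-randomisation reading; they do not carry over to the change from the pre-injection reading.

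It would go too far to conclude that comparing unadjusted changes is biased or inflates the type I error. Under randomisation it does neither, and chance imbalance costs precision only. The outcome is secondary, and the sample size makes no power claim for it.

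**What to change.** 1. In the section 2.1 flow chart, move the first blood pressure and pulse recording above the randomisation step, so that it is taken before the envelope is opened.
2. In section 2.13, state that the Mann-Whitney test applies to the pain scores.
3. Compare post-injection systolic pressure, diastolic pressure and pulse by ANCOVA, with arm as factor and the pre-randomisation reading as covariate. Report the adjusted difference in mmHg or beats/min with a 95% confidence interval.
4. Keep the stated outcome, the change from the pre-injection reading, as an unadjusted difference between arms with a 95% confidence interval. Do not use the pre-injection reading as the main covariate, because treatment may already have affected it.

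The cost is one moved line and a few sentences, with no new measurements or patients. The downsides are a linear-model assumption, which residuals can check, and one extra analysis to report.

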3 TRIAL ORGANISATION

3.1 SPONSORSHIP

The TENS-LA trial will be sponsored by University Hospitals of Leicester NHS Trust.

3.3 COLLABORATOR'S RESPONSIBILITIES

The responsibilities of the chief investigator will be detailed in advance of starting the trial and will include:

- Ensure all necessary approvals are in place prior to starting the trial
- Delegate responsibilities related to the trial only to suitably qualified and trained personnel
- Ensure that patients fulfilling eligibility criteria and considered for the trial
- Ensure patients are given adequate information regarding the trial and informed consent obtained
- Ensure that the documentation is up to date
- Ensure that all adverse effects related to the trial are promptly reported
- Ensure that the trial is conducted in accordance with the ICH GCP and fulfils local and national guidelines.
- Hold the responsibility for archiving the original trial documents for 5 years after end of trial

3.4 PUBLICATION AND DISSEMINATION OF RESULTS

The trial protocol and the final results of the trial will be published in established peer-reviewed journal. Links to the publication will be provided in all applicable trial registers. In addition, participants of the trial will be informed of the trial results if requested.

4 LIST OF ABBREVIATIONS

AE	Adverse Event
AR	Adverse Reaction
BP	Blood Pressure
EMLA	Eutectic Mixture of Local Anaesthetics
GCP	Good Clinical practice
ICD	Implantable Cardioverter Defibrillators
LA	Local Anaesthetic
PR	Pulse Rate
TAA	Theatre Arrivals Area
TENS	Transcutaneous Electronic Nerve Stimulation
UK	United Kingdom

Appendix 1: Patient Information Sheet

Appendix 2: Informed Consent Appendix 3: Case Report Form
